1.7. Utility as follow-up tool

Biopsies, the gold standard of liver health are not repeated as routine patient care and blood test results are not always indicative or sensitive enough to foresee deterioration in liver function in a timely manner.

A safe, non-invasive accurate test that assesses liver function and, when relevant, shows trends compared to previous breath tests, could highly improve patient management.

Preliminary data utilizing the MBT has demonstrated that the results from this system correlated with hepatic fibrosis in patients with chronic HCV and with the clinical course in patients pre and post transplantation and with fulminate hepatitis.

1.7.1. Hepatic Impairment Score Using the BreathID MBT

Exalenz has developed an algorithm for the scoring of hepatic impairment in patients suffering from a wide range of chronic liver diseases. The algorithm developed was named the "Hepatic Impairment Score" (HIS). The HIS is a probability score based on breath test and other demographic parameters. It was developed using logistic regression methodology. The linear predictor of the model selected is transformed into a probability score of disease severity. The HIS is intended to be used as the device output.

The use of the MBT test and its resultant continuous HIS for a particular patient enables the practitioner to assess the liver disease severity. This claim/label of the MBT is supported by several medical key opinion leaders (KOL).

Assessing the severity of chronic liver disease is important for following reasons:

- To make a timely decision to perform liver biopsy

| | |
|--|--|
| Exalenz Bioscience Ltd. | Last update on: April 01, 2015 |
| Protocol: The predictive value of the BreathID, ¹³ C-Methacetin breath test for Hepatic Decompensation; a retrospective analysis | Version Level: 1b |
| Document No.: CSD00074 | Page 10 of 23 |

- To aid in assessment of the risk of developing cirrhosis and its complications, including bleeding varices, infections, ascites, and hepatic encephalopathy.
- To decide when to initiate certain diagnostic investigations and therapeutic interventions including: Anti -viral treatment, upper endoscopy, use of beta blockers for varices and determination of frequency of monitoring of disease progression.
- To decide when to begin surveillance for liver cancer, such as blood tests (serum levels of alpha feto protein) and imaging (ultrasound).
- To decide when to prepare or list a patient for liver transplantation.

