1.4. Breath Tests

Breath tests that are based on monitoring the ¹³CO₂, which is a by-product of ¹³C labeled substrates metabolism by the liver, have been proposed as a tool for non-invasive evaluation of liver health and have been used for over 30 years.

Methacetin may be utilized for the evaluation of liver functional capacity and/or the extent of liver impairment. The biochemical basis for the evaluation of functional capacity is that the compound is metabolized by the cytochrome P450 enzyme CYP1A2. Diseases of the liver that cause a loss in functional mass and/or impact the metabolic function of CYP1A2 in hepatic microsomes hepatocytes are associated with and may be correlated to a decrease in the liver capacity to metabolize Methacetin.

One of the most common methods for determining the rate of metabolism of Methacetin is to analyze the rate of metabolism of the methoxy group (CH₃O) of Methacetin to carbon dioxide, which is excreted in exhaled breath. To distinguish the carbon dioxide derived from Methacetin from all other sources of carbon dioxide, the methoxy group is labeled with ¹³C, a stable isotope of carbon. Thus all the CO₂ derived from Methacetin will contain ¹³C (¹³CO₂) in contrast to all other sources of CO₂, which will contain approximately 99% ¹²C, and 1% ¹³C, the naturally abundant isotope. Thus, the rate of excretion of CO₂ (normalized

| | |
|--|--|
| Exalenz Bioscience Ltd. | Last update on: April 01, 2015 |
| Protocol: The predictive value of the BreathID, ¹³ C-Methacetin breath test for Hepatic Decompensation; a retrospective analysis | Version Level: 1b |
| Document No.: CSD00074 | Page 9 of 23 |

to CO₂) above background following the administration of Methacetin-methoxy-¹³C indicates its rate of metabolism, which relates to the hepatic cell "health" and to the functional mass of the liver.

1.5. BreathID® System:

Exalenz has developed the BreathID device to perform automatic breath tests based on a unique molecular correlation spectrometer (MCS). Based on specific optical-radiation emission and absorption by ¹³CO₂ and ¹²CO₂ gases, the portable BreathID MCS device continuously senses exhaled breath and analyzes CO₂ in real-time through a nasal cannula worn by the patient. The primary output of the BreathID is the PDR (percentage dose recovery) and CPDR (Cumulative PDR) which quantify the amount of ¹³C labeled substrate metabolized by the liver..

1.6. ¹³C-labeled substrate - ¹³C-Methacetin:

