Furthermore, if the second endpoint shows that the predictive value of MBT is greater than that of liver biopsy, many patients would be able to avoid the invasive nature and economically burdensome liver biopsy.

In consideration of the rationale and rating the benefits and risks, the conduct of this clinical trial is ethically justified.

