2. OBJECTIVES

The objectives of this study are:

- To evaluate the ability of the Methacetin Breath Test to detect hepatic decompensation events
- To evaluate the relationship between liver Biopsy and clinical outcome and show that the MBT has a better predictive ability of clinical outcome than liver biopsy.

| | |
|--|--|
| Exalenz Bioscience Ltd. | Last update on: April 01, 2015 |
| Protocol: The predictive value of the BreathID, ¹³ C-Methacetin breath test for Hepatic Decompensation; a retrospective analysis | Version Level: 1b |
| Document No.: CSD00074 | Page 12 of 23 |

- To evaluate the ability of the MBT to predict each of the individual liver related complications.

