8.2. Primary Endpoint

The MBT results and the time to hepatic decompensation events:

Hepatic decompensation event is defined as the occurrence of at least one of the following events in the time frame between the last ¹³C Methacetin Breath Test (MBT) to the time of data collection:

1. Death (liver related)
2. Transplantation (cadaveric and living donors)
3. Ascites
4. HE (Hepatic Encephalopathy)
5. Newly diagnosed varices or variceal bleeding
6. SBP (spontaneous bacterial peritonitis)/Sepsis
7. HRS (Hepatorenal syndrome)
8. HCC (Hepatocellular carcinoma)
9. Increase in CTP (Child Turcotte Pugh) Score by 3 points
10. Increase in MELD score by 5 points

.

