8.6. Statistical Analyses

All statistical analyses and data presentations, including tabulations and listings, will be performed using the SAS version 9.3 (or higher) software. Statistical tests will be two-sided and the level of significance is 0.05. Nominal p-values will be presented.

Baseline demographics and medical characteristics will be presented in tabular format. The statistical evaluation of baseline characteristics will include all available data.

For continuous variables, the following descriptive statistics will be given: N, Mean, Standard Deviation, Minimum, Median and Maximum values; for discrete variables, the Frequency and Percentage of patients or events will be provided.

For comparison of means (continuous variables), the two-sample t-test or the Wilcoxon rank sum test will be used as appropriate. For comparison of proportions (categorical variables), the Chi-squared test or Fisher's exact test will be used as appropriate.

Kaplan-Meier curves of the time event data will be presented. For comparison of time to event data, the log rank test will be used. Cox regression will be used to estimate hazard ratios, their level of significance and 95% confidence limits.

Risk stratification may be performed by categorizing the MBT into risk groups, for these groups Kaplan-Meier Curves of the time to clinical outcome will be presented for the MBT categories as well as the liver biopsy results to compare predictive value.

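### If HIS is the MBT measure, the comparison with biopsy sets a score containing demographics against biopsy with no covariates named, so part of any MBT advantage could come from demographics

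*Combined protocol and SAP*

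**What the plan says.** Section 1.7.1 describes HIS: "The HIS is a probability score based on breath test and other demographic parameters". On how it was built: "It was developed using logistic regression methodology". The linear predictor is turned into a probability of disease severity, and "The HIS is intended to be used as the device output". The variables and their weights are not listed.

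Section 1.5 gives a different primary output for the device, PDR and CPDR, which measure metabolised substrate and contain no demographics.

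The statistical section does not choose between them. Section 8.2 defines the endpoint as "The MBT results and the time to hepatic decompensation events".

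The comparative aim in section 2 is to "show that the MBT has a better predictive ability of clinical outcome than liver biopsy". Section 8.1 repeats it with biopsy/MELD as comparator. The comparison method in section 8.6 is optional risk grouping of the MBT, with Kaplan-Meier curves that "will be presented for the MBT categories as well as the liver biopsy results to compare predictive value". Cox regression is planned, but no covariates are named for either test, and no measure of the difference in prediction is given.

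Section 1.10 attaches the consequence: "if the second endpoint shows that the predictive value of MBT is greater than that of liver biopsy", many patients could avoid biopsy. Section 6.2.1 records demographic data.

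**The concern.** A composite score and a single histology result do not carry the same information. Suppose HIS is analysed and its demographic variables predict decompensation beyond what the breath test measures. HIS can then rank patients better than biopsy even when the breath test is no more informative than biopsy. The plan could not separate the two sources, because it has neither a breath-only comparison nor a biopsy model with the same demographics.

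The claim at stake is that the breath test predicts better than biopsy, which section 1.10 would use to support avoiding biopsy. A clinician reading a biopsy already knows the patient's demographics, so an advantage that comes from them is not evidence for the breath test over biopsy.

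**Working it through.** **The plan's own figure.** Section 8.5 gives a maximum of 414 + 165 = 579 subjects, which reproduces. It is a ceiling, not a power calculation. The documents give no C-index, effect size or power for MBT against biopsy, so there is no comparative figure to reproduce.

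**What has to be assumed.** The HIS variables and weights, the prognostic effect of demographics, and the accuracy of both tests. The simulations below show whether the mechanism works and over what range. They do not estimate its size in this study.

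**Set-up.** N = 579, 6 years of follow-up. Latent severity S ~ N(0,1). Breath = S + N(0, SD 0.6) and biopsy = S + N(0, SD 0.6), so the two tests are equally informative. One demographic variable D ~ N(0,1). Hazard = 0.02 × exp(0.8·S + b·D), with b = 0.3 (HR e^0.3 = 1.35 per SD) or b = 0.5 (HR e^0.5 = 1.65 per SD).

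**Step 1: HIS tuned to the outcome** (the best linear combination of breath and D for events, D independent of S).

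| HR of D per SD | Biopsy | Breath | HIS | Biopsy + D | HIS − biopsy | HIS − (biopsy + D) |
|---|---|---|---|---|---|---|
| 1.35 | 0.685 | 0.679 | 0.696 | 0.694 | 0.011 | 0.002 |
| 1.65 | 0.682 | 0.677 | 0.719 | 0.718 | 0.037 | 0.001 |

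Monte Carlo error is about 0.01. Breath and biopsy are identical by construction yet differ by 0.685 − 0.679 = 0.006, so the first gap is close to noise. A rerun of the outcome-tuned case gave gains of 0.02 to 0.04. The gain disappears once biopsy carries the same variable.

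**Step 2: HIS trained on severity**, which is how section 1.7.1 describes it (logistic regression on a biopsy-defined severity class; the cut-off is an assumption).

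| Demographic variable | C-index gain of HIS over biopsy alone |
|---|---|
| Independent of severity, HR 1.35 | 0.678 − 0.680 = −0.002 (HIS higher in 48% of replicates) |
| Independent of severity, HR 1.65 | 0.675 − 0.673 = 0.002 (HIS higher in 51%) |
| Correlated 0.3 with severity, acting only through it | 0.682 − 0.682 = 0 |
| Correlated 0.3 to 0.5 with severity and independently prognostic | about 0.007 to 0.02 |

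A severity model gives almost no weight to a variable unrelated to severity, so the first two rows are zero within noise. A gain needs a demographic variable that is related to severity and also predicts events independently of it.

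**Step 3: does giving biopsy the demographics make the comparison fair?** Not if HIS stays fixed. In the Step 2 scenarios with an independently prognostic variable, a biopsy-plus-demographics model refitted to the outcome beat the fixed, severity-trained HIS in about 69% to 97% of replicates, although the tests were equal. The demographics must therefore be fitted in the same way on both sides.

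**The case against.** **HIS may not be the measure analysed.** No endpoint, objective or analysis names it. It appears only in the background, and section 1.5 calls PDR and CPDR the primary output. This stands, and the point is conditional on it. But section 1.7.1 names HIS as the intended device output and nothing excludes it. Choosing HIS would settle the measure and leave the comparison unmatched.

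**Biopsy assessed without covariates is inferred from silence.** This also stands: section 8.6 names no covariates for either test. Silence is still enough to leave the comparison uncontrolled.

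**Comparing the device as used with biopsy as reported is legitimate.** It is, and it can be reported. It answers whether the device output ranks patients better, not whether the breath test does.

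**Stronger readings to avoid.** A reader might infer that the breath test adds nothing. That does not follow: in Step 1 breath alone scores about the same as biopsy, and what fails is the claim of being better. A reader might also expect a large bias. A separate simulation with freely chosen weights and a demographic HR of 2.0 per SD gave 0.715 for HIS against 0.633 for biopsy, a gap of 0.08. The documents supply neither that effect nor those weights, and they describe a score built for severity. With a non-prognostic demographic variable (HR 1.0, weight 0.4), the same simulation put HIS below biopsy, 0.632 against 0.640.

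**Conclusion.** The concern holds conditionally. If HIS is the MBT measure, the planned comparison cannot attribute an advantage over biopsy to the breath test, because only one side is known to contain demographics. If PDR or CPDR is used, the problem does not arise.

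The size cannot be computed from the documents. With equally informative tests and assumed demographic HRs of 1.35 to 1.65 per SD, the C-index gain is 0 when the demographic variable is independent of severity or acts only through it. It reaches about 0.02 for a severity-trained HIS and about 0.04 for a score tuned to the outcome. The documents do not show that such a gain will occur. They show that the plan could not recognise it. The correction is cheap and should be made before the analysis, given the use that section 1.10 would make of the result.

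**What to change.** Add to section 8.6:

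*The MBT and biopsy are compared in patients with both a valid MBT and a valid biopsy. Two comparisons are reported: (a) the breath-only measure (PDR or CPDR, named in advance) against biopsy alone; (b) a Cox model for the MBT and a Cox model for biopsy, both including the same demographic variables, namely those that enter HIS, fitted in the same way to the same events. In each, the difference in C-index is given with a 95% bootstrap confidence interval. HIS as issued against biopsy may also be reported as the device-as-used comparison. The statement that the breath test predicts better than biopsy rests on (a) and (b).*

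The sponsor must list the variables that enter HIS, since the protocol does not. The breath measure should enter (b) directly; a fixed HIS should not be set against a refitted biopsy model (Step 3).

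Cost: SAP wording, one or two extra Cox models and a few parameters, using demographics already recorded. The paired set may be smaller than 579, because section 5 admits patients without a valid biopsy; its size is not stated. The stated MBT advantage may also be smaller.

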1.7.2. Biopsy Scoring

Repeat biopsy scoring, where available, will be collected according to the standard scoring procedure at each site. The study itself does not call for additional biopsies to be carried out.

1.8. Safety and Efficacy of the Investigational Product

Information on the Safety of the Investigational New Drug and safety and efficacy of the MBT and the BreathID device are provided in the Investigator Brochure, though no safety issues are expected since this is a retrospective non-interventional study.

1.9. Rationale for the Current Study

Timely assessment of disease progression associated morbidity and mortality is important for educated/proper management of cirrhotic patients. For example:

- Instrumental in determining the long-term prognosis of the patient
- Establishing the risk for hepatic complications in chronic liver patients regarding conditions that are common in these patients, such as portal hypertension and subsequent esophageal varices and cancer.
- Cirrhosis often is an indolent disease/condition; many of the patients remain asymptomatic until the occurrence of decompensation, characterized by ascites, spontaneous bacterial peritonitis, hepatic encephalopathy or variceal bleeding from portal hypertension. Thus, early diagnosis of patients at higher risk for such complications may lead to treatment that can prevent development of these complications and others such as hepatocellular carcinoma, overt encephalopathy and liver decompensation after surgery.

1.10. Summary of Overall Risk and Benefits

Since this proposed study is retrospective no adverse events and/or risk associated with the MBT are expected.

The MBT BreathID system consists of the device and ¹³C-Methacetin. The same device but with a different substrate (¹³C-Urea) for the diagnosis of H. Pylori was cleared as a 510(K). The software of the cleared device was upgraded in order to allow the BreathID system to be used in the assessment of liver disease severity. Therefore, the BreathID device does not pose any increased risk to patients participating in this study.

| | |
|--|--|
| Exalenz Bioscience Ltd. | Last update on: April 01, 2015 |
| Protocol: The predictive value of the BreathID, ¹³ C-Methacetin breath test for Hepatic Decompensation; a retrospective analysis | Version Level: 1b |
| Document No.: CSD00074 | Page 11 of 23 |

The ¹³C-methacetin substrate has been used for various breath tests in numerous patients including special populations such as neonatals and pregnant women. To the best of our knowledge no adverse events had ever been reported using ¹³C-Methacetin.

Furthermore, Methacetin is a well known drug that has been available and described in literature for over 30 years and is currently used in medications (such as acetaminophen) for human therapeutic use. No risks have been reported in literature using much higher doses of Methacetin than currently used in the MBT.

During the test procedure, patient contact with the device is through a nasal cannula for collection and analysis of the breath samples. Nasal breathing cannulae are a well-known and proven medical tool having minimum side effects. No discomfort has been reported during prior feasibility studies conducted by Exalenz involving over 400 patients performed with the nasal cannula.

The data analyzed in this study will be used to validate the hypothesis claiming a single ¹³C-Methacetin breath test in chronic liver patients may correlate with liver related morbidity and mortality. This claim had been already been demonstrated in previous studies done by the company, showing a hazard ratio of up to 12 between a single MBT and complications and mortality in chronic patients within one year of the breath test. If such a claim is to be validated, it is expected to influence the clinical practice for such patients preventing the onset of complications and death.

Furthermore, if the second endpoint shows that the predictive value of MBT is greater than that of liver biopsy, many patients would be able to avoid the invasive nature and economically burdensome liver biopsy.

In consideration of the rationale and rating the benefits and risks, the conduct of this clinical trial is ethically justified.

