| Document No.: CSD00074 | Page 3 of 23 |

| | | |
|---------|--|----|
| 8. | STATISTICAL CONSIDERATIONS..... | 15 |
| 8.1. | STUDY DESIGN AND OBJECTIVES..... | 15 |
| 8.2. | PRIMARY ENDPOINT | 15 |
| 8.3. | SECONDARY ENDPOINT | 15 |
| 8.4. | SAFETY ENDPOINTS | 15 |
| 8.5. | SAMPLE SIZE..... | 15 |
| 8.6. | STATISTICAL ANALYSES..... | 16 |
| 9. | ADVERSE EVENTS..... | 16 |
| 10. | STUDY ADMINISTRATION..... | 16 |
| 10.1. | REGULATORY AND ETHICAL CONSIDERATIONS | 16 |
| 10.1.1. | Informed Consent | 16 |
| 10.1.2. | Institutional Review Board | 16 |
| 10.1.3. | End of the study | 17 |
| 10.2. | INVESTIGATOR RESPONSIBILITIES | 17 |
| 10.3. | DATA MANAGEMENT | 17 |
| 10.4. | STUDY MONITORING | 17 |
| 10.5. | SUBJECT CONFIDENTIALITY | 17 |
| 10.6. | QUALITY ASSURANCE..... | 18 |
| 10.7. | RETENTION OF ESSENTIAL STUDY DOCUMENTS | 18 |
| 10.8. | AGREEMENTS..... | 18 |
| 11. | PUBLICATION | 18 |
| 12. | REFERENCES..... | 18 |

| | |
|--|--|
| Exalenz Bioscience Ltd. | Last update on: April 01, 2015 |
| Protocol: The predictive value of the BreathID, ¹³ C-Methacetin breath test for Hepatic Decompensation; a retrospective analysis | Version Level: 1b |
| Document No.: CSD00074 | Page 4 of 23 |

SYNOPSIS

Investigational Product:

0.05% ¹³C-Methacetin solution and the BreathID® Device

Phase of Development:

Retrospective clinical investigation

Background:

This study is a follow up study to be conducted in selected sites, that participated in Exalenz' Pivotal HIS-EX-408 and/or PLT-BID-1108 study using the MBT in chronic liver patients. The aim of the study was to compare the breath test to the liver biopsy to assess the capability to detect cirrhosis.

Study Rationale:

Previous studies have shown that the MBT can be used to predict liver decompensation. In the present study Exalenz wishes to evaluate the prognostic value of MBT and Biopsy in a long term retrospective surveillance of the described study population.

Objectives:

To evaluate the ability of the MBT to predict hepatic decompensation events, in patients with chronic liver disease.

Primary outcome measures: MBT results and Hepatic decompensation measured with the time to each event, defined as the occurrence of at least one of the following events in the time frame between the last ¹³C-Methacetin Breath Test (MBT) to the time of data collection:

1. Death (liver related)
2. Transplantation (cadaveric and living donors)
3. Ascites
4. HE (Hepatic Encephalopathy)

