5. Newly diagnosed varices or variceal bleeding
6. SBP (spontaneous bacterial peritonitis)/Sepsis
7. HRS (Hepatorenal syndrome)
8. HCC (hepatocellular carcinoma)
9. Increase in CTP (Child Turcotte Pugh) Score by 3 points
10. Increase in MELD score by 5 points

Primary Endpoints:

Time to the first occurrence of a hepatic decompensation event (as defined in the primary outcome measures).

Secondary endpoints:

| | |
|--|--|
| Exalenz Bioscience Ltd. | Last update on: April 01, 2015 |
| Protocol: The predictive value of the BreathID, ¹³ C-Methacetin breath test for Hepatic Decompensation; a retrospective analysis | Version Level: 1b |
| Document No.: CSD00074 | Page 5 of 23 |

- Histological liver biopsy results (obtained in the initial study) versus clinical outcome at time of current data collection
- Time to each of the individual events as follows:
 1. Death (liver related)
 2. Transplantation (cadaveric and living donors)
 3. Ascites
 4. HE (Hepatic Encephalopathy)
 5. Newly diagnosed varices or variceal bleeding
 6. SBP (spontaneous bacterial peritonitis)/Sepsis
 7. HRS (Hepatorenal syndrome)
 8. HCC (hepatocellular carcinoma)
 9. Increase in CTP (Child Turcotte Pugh) Score by 3 points.
 10. Increase in MELD score by 5 points

Study Design: Retrospective, multicenter clinical evaluation of patients' outcome initially enrolled (n=414+165=579) into the Exalenz pivotal studies (protocols HIS-EX-408 and/or PLT-BID-1108 respectively). The information collected in this study will be anonymous.

Study Population: A maximum of 579 adult male or female patients enrolled into the Exalenz studies (protocols HIS-EX-408 and/or PLT-BID-1108) who performed a ¹³C-Methacetin Breath Test.

Main Inclusion Criteria: Patient has been tested with the MBT in the past Exalenz pivotal studies protocols HIS-EX-408 and/or PLT-BID-1108 (from August 2008 to September 2012).

Main Exclusion Criteria: Patient had been enrolled into the pivotal study but not included in the final analysis due to conditions / factors interfering with the MBT (i.e. exclusion criteria within the HIS-EX-408 and/or PLT-BID-1108 study).

Statistical Analysis:

Introduction:

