It is anticipated that 3-5% of patients with stable cirrhosis will develop hepatic decompensation and achieve an end-point within a year. An additional 1-2% would be expected to die from these complications per year. This study is conducted 6 years post initial enrollment, accordingly the expected amount of complications are expected to be 6 times higher. Furthermore some of the patients that were not considered as cirrhotic at the time of enrollment may progress to cirrhosis and deteriorate.

| | |
|--|--|
| Exalenz Bioscience Ltd. | Last update on: April 01, 2015 |
| Protocol: The predictive value of the BreathID, ¹³ C-Methacetin breath test for Hepatic Decompensation; a retrospective analysis | Version Level: 1b |
| Document No.: CSD00074 | Page 6 of 23 |

All patients with valid breath test results from the HIS-EX-408 and/or PLT-BID-1108 trials will be candidates for this follow up trial.

Analyses:

All statistical analyses and data presentations, including tabulations and listings, will be performed using the SAS version 9.3 (or higher) software. Statistical tests will be two-sided and the level of significance is 0.05. Nominal p-values will be presented.

The ability of MBT to predict morbidity and mortality and other complications will be evaluated using survival analysis methods, mainly Kaplan-Meier curves and Cox regression analyses.

| | |
|--|--|
| Exalenz Bioscience Ltd. | Last update on: April 01, 2015 |
| Protocol: The predictive value of the BreathID, ¹³ C-Methacetin breath test for Hepatic Decompensation; a retrospective analysis | Version Level: 1b |
| Document No.: CSD00074 | Page 7 of 23 |

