3. ENDPOINTS

3.1. Primary Efficacy Endpoints

The MBT results and the time to hepatic decompensation events:

Hepatic decompensation is defined as the occurrence of at least one of the following events in the time frame between the last ¹³C-Methacetin Breath Test (MBT) to the time of data collection:

1. Death (liver related)
2. Transplantation (cadaveric and living donors)
3. Ascites
4. HE (Hepatic Encephalopathy)
5. Newly diagnosed varices or variceal bleeding
6. SBP (spontaneous bacterial peritonitis)/Sepsis
7. HRS (Hepatorenal syndrome)
8. HCC (hepatocellular carcinoma)
9. Increase in CTP (Child Turcotte Pugh) Score by 3 points
10. Increase in MELD score by 5 points

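### The cited MBT hazard ratio applies within one year, but section 8.6 plans Cox hazard ratios over about 2.5 to 6.7 years with no time horizon and no proportional-hazards check

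*Combined protocol and SAP*

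**What the plan says.** **Earlier result.** Section 1.10 (Summary of Overall Risk and Benefits) says the data will serve to validate the hypothesis that a single "breath test in chronic liver patients may correlate with liver related morbidity and mortality". That hypothesis has no time horizon. The support cited for it does: a "hazard ratio of up to 12 between a single MBT and complications and mortality in chronic patients within one year of the breath test". No MBT cut-off, unit or confidence interval accompanies the figure.

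**Aim of this study.** The Synopsis (Study Rationale) wants to "evaluate the prognostic value of MBT and Biopsy in a long term retrospective surveillance". Section 8.1 adds a comparative objective: to show that MBT predicts time to these events better than liver biopsy or MELD.

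**Follow-up.** The Synopsis (Main Inclusion Criteria) dates the breath tests "from August 2008 to September 2012". Section 3.1 runs the event window from the last MBT "to the time of data collection", without a calendar date or a common cut-off. The Synopsis (Statistical Analysis, Introduction) says "This study is conducted 6 years post initial enrollment". The page header reads "Last update on: April 01, 2015".

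**Analysis.** Section 8.6 plans Kaplan-Meier curves and log-rank tests, and says "Cox regression will be used to estimate hazard ratios, their level of significance and 95% confidence limits". Grouping patients by MBT risk is optional there. Where it is done, curves for the MBT groups and for biopsy are to be shown to compare predictive value.

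**The concern.** The only effect size that the protocol offers for MBT describes the first year after the test. The planned hazard ratio covers several years, and patients differ about 2.7-fold in potential follow-up. A single baseline test may become less informative as the liver changes: the Synopsis itself expects some patients who were not cirrhotic at enrolment to progress. Section 8.6 neither assumes a constant effect openly nor checks for one.

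Two questions are at stake. The first is how the result relates to the one-year figure. An overall hazard ratio near 5 could come from a strong early effect that fades or from a constant moderate one, and the planned estimate alone cannot separate the two. The second is how long a single test stays informative, which matters for a study described as long-term.

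**Working it through.** **1. The plan's own figure.** Section 8.5 gives a maximum of 579 subjects: 414 + 165 = 579. This reproduces. The documents state no power, target hazard ratio or required number of events.

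**2. Potential follow-up.** Assumption: data are collected on the protocol date, 1 April 2015.
- First tests, 1 to 31 August 2008: 6.66 to 6.58 years.
- Last tests, 1 to 30 September 2012: 2.58 to 2.50 years.
- Ratio of the extremes: 6.66 / 2.50 = 2.7.

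The figure of 6.7 years is derived here and does not stand in the documents. Later data collection would lengthen every patient's follow-up.

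**3. What one Cox hazard ratio estimates.** For a binary MBT group, the large-sample Cox estimate is exp(b), where b solves

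∫ { d₁(t) − [d₁(t) + d₀(t)] · n₁(t)eᵇ / [n₁(t)eᵇ + n₀(t)] } dt = 0.

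Here n₁ and n₀ are the proportions at risk in the poor-MBT and other groups, and d₁ and d₀ are their event rates.

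Inputs:
- Hazard ratio in year 1: 12, the cited maximum.
- Hazard ratio after year 1: 1.5 to 4 (assumed), with a constant 12 as the comparison case.
- Share with poor MBT: one third (assumed).
- Event rate in the other group: 0.5% to 2% per year (assumed). The implied first-year risk overall is (2/3)(1 − e^(−λ)) + (1/3)(1 − e^(−12λ)), which is 2.3% at λ = 0.005, about 4.4% at 0.01 and 8.4% at 0.02. The Synopsis gives 3–5% per year for stable cirrhosis, so the lower rates are the closer match.
- Follow-up: everyone stopped at 2.5 years, or spread uniformly from 2.5 to 6.66 years (assumed).

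| Later HR | Single HR, stopped at 2.5 years | Single HR, 2.5 to 6.66 years |
|---|---|---|
| 1.5 | 5.7–5.9 | 3.8–4.0 |
| 4 | 7.2–7.3 | 5.8–5.9 |
| 12 (constant) | 12.0 | 12.0 |

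The range in each cell comes from the event rate, which hardly matters.

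**4. Sensitivity to the group share.** This run used a share of 25% to 50%, a first-year risk of 3–5%, a later hazard ratio of 3 and an upper follow-up limit of 6.67 years. The single hazard ratio is 12.0 at 1 year, 6.5–6.6 at 2.58 years, 5.0–5.1 over 2.5 to 6.67 years and 4.4–4.5 if all are followed for 6.67 years. So 12 followed by 3 gives about 5, and so does a constant hazard ratio of 5.

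**5. Can year 1 be analysed on its own?** If 3–5% applied to all 579, year-1 events would number 579 × 0.03 = 17 to 579 × 0.05 = 29. This is an upper range, because the rate is stated for stable cirrhosis only. To detect a hazard ratio of 12 with 80% power at two-sided 0.05, using (1.96 + 0.84)² = 7.85:
- Schoenfeld, 50% share: 7.85 / [0.25 × (ln 12)²] = 5.1, so 6 events.
- Schoenfeld, 25% share: 7.85 / [0.1875 × (ln 12)²] = 6.8, so 7 events.
- Freedman: 7.85 × (13/11)² = 10.96, so 11 events.

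An effect of the cited size could be detected. A smaller one would be estimated imprecisely.

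**The case against.** The strongest reply is that section 8.6 answers the hypothesis as written. That hypothesis states an association and no horizon. The one-year figure is earlier support in a risk-benefit section, and it is not used in the objectives, the endpoints or the sample size. The stated aim is long-term, and an overall Cox hazard ratio addresses it. This stands. A reader might infer that the whole MBT claim depends on the one-year hazard ratio, and the text does not say so.

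A reader might also infer that the planned estimate does mix early and late effects and does depend on follow-up length. The documents do not support that as a fact. It holds only if the effect changes with time, and under a constant effect the estimate is the same at every length. Expected progression in some patients makes a fading effect plausible, but no data on it are given.

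A third tempting reading is that a year-1 hazard ratio would confirm or refute the figure of 12. It could not do so formally: the earlier figure is a maximum, with no cut-off, unit or interval.

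It is also fair that Kaplan-Meier curves would show timing, and that a single hazard ratio is inferred from silence, since section 8.6 uses the plural without dividing it by time. But the curves are descriptive with no named time points, and the grouping by MBT is optional. What remains is that nothing in the plan would detect or describe a changing effect.

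**Conclusion.** The gap is real and moderate, and closing it is a cheap improvement. The planned Cox analysis is valid as an average. As written, it cannot be related to the one-year result or show how long one test stays informative.

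The size depends on assumptions. With a hazard ratio of 12 in year 1 and 1.5 to 4 later, the single estimate would be about 3.8 to 5.9 over staggered full follow-up and 5.7 to 7.3 at 2.5 years. With a constant 12 there is no distortion. The later hazard ratios, the share with poor MBT, the event rate, uniform follow-up and data collection at the protocol date are all assumed. The documents give none of them for this cohort as a whole.

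**What to change.** In section 8.6:

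1. Keep the overall Cox hazard ratio as the main estimate.
2. Pre-specify a proportional-hazards check for MBT. As supportive analyses, give separate hazard ratios for year 1 and after year 1 from a piecewise Cox model.
3. Report a time-dependent AUC or C-index at 1, 3 and 5 years for MBT, biopsy and MELD, in patients who have all three measures. This also serves the comparative objective in section 8.1, for which section 8.6 now offers only optional curves, and none for MELD.
4. Present the year-1 hazard ratio as context for the earlier figure and not as a formal test of it.

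The cost is plan wording and standard SAS code, with no new data. The downside is fewer events per period and so wider intervals: year 1 would have at most about 17 to 29 events. With data collection at the protocol date, only patients tested by 1 April 2010 have 5 years of potential follow-up (1 April 2015 minus 5 years), so the 5-year estimates rest on the earlier-tested patients.
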